16.2. Case Report Form (CRF)

NOVAGENIX will design the Case Report Form in close co-operation with the Sponsor. Standardized CRFs will be used as **source document regarding** volunteers' raw data during the course of the study. The investigator will assure that all data are entered promptly, legibly, completely, accurately and in accordance with other source documents (**e.g. ECGs, laboratory results, diet and fluid intake records**). This procedure will be applied to the data of both volunteers who met the inclusion criterion and will be included into the study and the volunteers that will not be included into the study because of a valid reason.

To ensure legibility, the CRFs should be filled out only with a blue ball-point.

Any corrections to the CRFs must be carried out by the investigator or his designate. A single stroke must be drawn through the original entry. The reason for the correction has to be given and it has to be dated and initialled. Incorrect entries must not be covered with correcting fluid, or obliterated, or made illegible in any way.

Even if there are no changes from a previous examination, in the interests of completeness of data acquisition, the questions which are repeated in each section of the CRFs should be answered in full text. A reasonable explanation must be given by the investigator for all missing data.

The CRFs will be completed immediately after termination of the individual treatment and observation periods and the final examination. After being signed by the investigator, they will be sent to NOVAGENIX for data validation. Thereafter, CRFs will be returned to NOVAGENIX and eventually forwarded to the Investigator for final corrections, if applicable. CRFs can not be sent by post but only be personally submitted to the NOVAGENIX monitor during a visit or sent by courier. Any other way of transport is to be previously discussed with the NOVAGENIX. NOVAGENIX will send the original CRFs to Sponsor with the final report of the study. NOVAGENIX will store the copy of all CRFs.

All medical records upon which the CRFs are based must be kept for **at least 14 years** after completion of the study. At this time **ALPAN Farma** will discuss with the Sponsor whether or not storage is required for a longer period. Image carriers or other data carriers can be used for the purpose of storage.

17. ANALYTICAL EVALUATION

Plasma concentrations of **lopinavir and ritonavir** will be determined by means of a validated LC method, according to Novagenix's SOP NOV-ENG-08-TEC1.

Detailed characteristics of the analytical method applied will be described in the "Analytical Study Plan" (see **Appendix III: Analytical Study Plan**). *All assay validations will be performed in consideration of the Guideline on Bioanalytical Method Validation, EMA, 21 July 2011 and US FDA Guidance for Industry, Bioanalytical Method Validation May 2018 or current guidance on method validation date.*

Volunteer's all samples will be measured in a single analytical run in order to eliminate the influence of the inter-assay variance on the assessment. The analyst has to provide a final analytical report with tables for all samples that were analysed.

Already measured samples will be stored at $<-20^{\circ}\text{C}$ for at least 6 months (storage period can be prolonged in exceptional cases, e.g. upon special request of authorities) after termination of bio-analysis. At that point a further decision by the Sponsor will be taken.

20% of the chromatograms are to be included in printed Final Study Report. But 100 % of chromatograms will be given also as electronically.

17.1. Reanalysis of study samples

The reasons for reanalysis of study samples are presented in **Appendix III: Analytical Study Plan**.

17.2. Incurred Sample Reanalysis

Incurred Sample Reanalysis (ISR) will be performed at any time after starting subject analysis by choosing two sampling points near or at C_{max} and two sampling points in the elimination phase per period (total 16 sampling points per subject). These ISR points will be selected according to the literatures and/or in the very first batches of subject analysis. The subjects will be randomly selected and the number of subjects that defined as ISR points will be equal or more than 10% of samples for the first 1000 study samples and an additional 5% of samples for study samples in excess of 1000. The difference between the study samples' and incurred samples' values obtained should be within 20% of the mean for at least 67% of the repeats according to EMEA/CHMP/EWP/192217/2009 Rev.1 Corr.2. Guideline on Bioanalytical Method Validation. London, 21 July 2011, p.13-14; Novagenix's SOP-NOV-ENG-08-CQU4 and documented in the Final Study Report.

18. PHARMACOKINETIC EVALUATION

Pharmacokinetic parameters of **lopinavir and ritonavir** will be determined using non-compartmental methods from measured plasma concentrations.

For each treatment (**Test Drug** or **Reference Drug**) and each volunteer participating completely in this **single-dose, four-period, full-replicated, cross-over study** the following pharmacokinetic parameters will be calculated:

Primary pharmacokinetic parameters:

C_{max}: Maximum observed plasma concentration

AUC_{0-last}: Area under the plasma concentration-time curve from zero to the last measurable concentration, calculated by the linear log trapezoidal rule.

Secondary pharmacokinetic parameters:

AUC_{0-∞}: Area under the plasma concentration-time curve, calculated by extrapolation to infinity.

t_{max}: Time to maximum observed plasma concentration

t_{1/2}: Terminal half-life

Additional pharmacokinetic parameters:

MRT: Mean residence time

λ_z: Terminal rate constant.

For pharmacokinetic calculations, the program package **Phoenix WinNonlin (Version 8.1, Certara L.P.)** or above will be employed. Phoenix WinNonlin will also be used to generate concentration/time plots.

19. STATISTICAL PROCEDURES

The statistical analysis of the pharmacokinetic data described in this section corresponds with provisions given by the CPMP guideline CPMP/EWP/QWP/1401/98 Rev. 1 dated 20 January 2010.

Statistical analysis will be performed as a valid case analysis including all volunteers in which no major protocol deviations occurred and all primary target variables are available for measurement.

If a volunteer is to be excluded from evaluation, this decision has to be justified in the Final Study Report. Statistical analysis will be performed by means of the program **Phoenix WinNonlin (Version 8.1, Certara L.P.)** or above.

19.1. Target Variables

19.1.1. Primary Target Variables

C_{\max} and $AUC_{0-t_{\text{last}}}$ are declared to be primary target variables.

19.1.2. Secondary Target Variables

$AUC_{0-\infty}$, t_{\max} and $t_{1/2}$ are declared to be secondary target variables. MRT and λ_z will be determined also.

19.1.3. Criteria for Bioequivalence

Bioequivalence of **Test Drug** in comparison with **Reference Drug** will be evaluated (T vs R) and concluded if the 90% confidence intervals for the geometric mean ratios of the treatments are fully contained within acceptance ranges for C_{\max} and $AUC_{0-t_{\text{last}}}$ for **lopinavir** and **ritonavir**.

The acceptance ranges for C_{\max} will be widened to a maximum of 69.84 -143.19% using scaled-average-bioequivalence (SABE) and for $AUC_{0-t_{\text{last}}}$ will be taken as 80.00-125.00% regardless of variability according to the EMA guideline (Guideline on the Investigation of Bioequivalence-CPMP/EWP/QWP/1401/98 Rev. 1/Corr, London 20 January 2010).

The extent of the widening is defined, as below, based upon the intra-subject coefficient of variation of Reference Drug (CV_{WR}):

- If CV_{WR} for C_{\max} is greater than 30%:

Acceptance ranges will be determined using scaled-average-bioequivalence (SABE) according to: $[U, L] = \exp [\pm k \cdot s_{WR}]$, where U is the upper limit of the acceptance range, L is the lower limit of the acceptance range, k is the regulatory constant set to 0.760, and s_{WR} is the intra-subject standard deviation of the log-transformed values of C_{\max} of the Reference product. s_{WR} will be obtained from Linear Mixed Effects model including only data for the Reference product with the subject effect (nested within sequence), the period at which it is given, the sequence in which each product is received as fixed effects.

Before CV_{WR} calculation for C_{\max} , to show the calculated intra-subject variability is a reliable estimate and that it is not the result of outliers, outlier analysis using studentized intrasubject residual will be applied to reference product data.

The table below gives examples of how different levels of variability lead to different acceptance limits using this methodology;

Within-subject CV (%)*	Lower Limit	Upper Limit
30	80.00	125.00
35	77.23	129.48
40	74.62	134.02
45	72.15	138.59
≥50	69.84	143.19

$$* CV(\%) = 100\sqrt{e^{\frac{2}{5n}} - 1}$$

The other criteria for SABE: The geometric mean ratio should lie within the conventional acceptance range 80.00- 125.00% for C_{\max} and $AUC_{0-\text{last}}$.

- If CV_{WR} is equal or less than 30%:

Assessment of bioequivalence will be determined using average bioequivalence methods. 80.00-125.00% acceptance range will be used for the assessment of bioequivalence.

For both conditions, in order to achieve a better approximation to a normal distribution C_{\max} and AUCs data will be logarithmically transformed (base e) before analysis. The terms to be used in Analysis of Variance (ANOVA) model are sequence, subject within sequence, period and treatment.

From the result of this procedure, the two one-sided hypothesis at the 5% level of significance will be tested by constructing the 90% confidence intervals for the ratios test versus reference preparation. The confidence intervals are calculated by retransformation of the shortest confidence intervals for the difference of the ln-transformed mean values.

Differences in t_{\max} will be evaluated non-parametrically.

Evaluating excluding values from statistical calculations, the criteria which are given in “Novagenix SOP-NOV-ENG-08-CQU5” will be applied.

These criteria are;

1. If a suspicious case about safety of blood samples such as in the absence of label, label is not read exactly or any confusion of sample, these samples are documented on “Protocol For Handing Over Receipt of Samples” form. These samples are analysed but not included in statistics.
2. After completing study analysis, reanalysis is done due to analytical reason according to SOP-NOV-ENG-08-TEC1 and SOP-NOV-ENG-08-CQU4. If the reanalysed data is still invalid for the analytical reason and there is insufficient plasma sample for reanalysis, that data should be excluded from statistical analyses. Any exclusion should be properly reported on final study report.
3. A subject with lack of any measurable concentrations or only very low plasma concentrations for reference medicinal product. A subject is considered to have very low plasma concentrations if its AUC is less than 5% of reference medicinal product geometric mean AUC (which should be calculated without inclusion of data from the outlying subject). That subject will be evaluated and may be excluded. Accordingly the two results are reported in final study report.
4. Subjects with non-zero baseline concentrations > 5% of C_{\max} . Such subject should be excluded from statistical calculation.
5. Total number of subject should not be under 12 in the statistical calculation, whether not this study would be repeated from the clinic part.

19.1.4. Safety Evaluation

The assessment of safety will be based mainly on the frequency of AEs and on the number of laboratory values that fall outside of pre-determined ranges. Other safety data (e.g. electrocardiogram, vital signs and special tests) will be considered as appropriate.

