10. DESIGN

In this open-label, randomised, single-dose, two-sequence, two treatment, four-period, full-replicated, cross-over study, **30 healthy** male subjects (intention to treat population) will receive one single oral dose of **200 mg lopinavir and 50 mg ritonavir [either one tablet of the test drug or one tablet of the reference drug according to the randomisation table]** under fasting conditions, according to a sequence determined by randomisation [in Period II and Period IV, the subjects will be administered by the other drug that they will not administered in the Period I and Period III].

Data of the subjects who have completed the study according to the Clinical Study Protocol will be used for analytical, pharmacokinetic and statistical evaluation.

Test Drug: “Orvical 200 mg/50 mg Film Tablet” is manufactured by World Medicine İlaç San. ve Tic. A.Ş., Turkey and is will be licensed by World Medicine İlaç San. ve Tic. A.Ş., Turkey.

Reference Drug: “Kaletra 200 mg/50 mg Film Kaplı Tablet” is manufactured by AbbVie Deutschland GmbH & Co. Germany and is licensed by AbbVie Tıbbi İlaçlar Sanayi ve Ticaret Limited Şirketi-İstanbul, Turkey

In study period, the subjects will be admitted to the FARMAGEN Clinical Unit in the evening (18:00) prior to morning of the administration of medication after **screening and isolation period as described in Appendix 7.**

Volunteers will be confined to the clinical unit and dosing will occur under conditions of hospitalization. Medications will be orally administered at approximately at 8:00 (t=0) after an overnight fasting (at least 10 hours in fasting). The lunch will be 4 hours post dosing and the dinner will be 10 hours post dosing. Blood sampling for the determination of **lopinavir and ritonavir** plasma concentrations will be drawn at specified time points. After taking the last blood sample and carried out the post-study examination, the subjects will be allowed to leave the clinic.

An overview of the study procedures is given in the Study Flow Chart provided in section 6.

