11. SELECTION OF VOLUNTEERS

11.1. Inclusion Criteria

Only volunteers fulfilling all of the following criteria should be enrolled in the present trial:

1. Healthy Caucasian male subjects aged between **20 and 40** years,
2. Non smokers or smoking maximum 5 cigarettes a day, those who won't smoke or drink coffee during the study period,
3. **Negative Covid-19 Rapid Test results and two Negative Covid-19 PCR test results,**
4. Negative alcohol breath test results,
5. Normal physical examination at screening visit,
6. Having the Body Mass Index ranged between **18.5-30 kg/m²** (see Appendix I) which is in the desirable range according to the age,
7. Ability to communicate adequately with the investigator himself or his representatives,
8. Ability and agreement to comply with the study requirements,
9. Normal blood pressure and heart rate measured under stabilised conditions at the screening visit after at least 5 minutes of rest under supine position: SBP within 100 to 140 mmHg, DBP within 60 to 90 mmHg and HR within 50 to 90 bpm,
10. Normal/ acceptable 12-lead electrocardiographic results at least after 5 minutes of rest,
11. Laboratory results within normal range or clinically non-significant (CBC, glucose, urea, uric acid, creatinine, *estimated GFR (eGFR)*, total bilirubin, sodium, potassium, calcium, chloride, SGOT (AST), SGPT (ALT), GGT, alkaline phosphatase, total protein and urinalysis), drug addiction scanning in urine results in negative (amphetamine, barbiturate, benzodiazepine, cannabinoid, cocaine, opiate),
12. Understanding of the study and agreement to give a written informed consent according to section 20.3.

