14.1. Withdrawal of Volunteers

Volunteers may be withdrawn for the following reasons:

- at their own request with or without giving reasons,
- at the discretion of the investigator for reasons of medical prudence.

In either event, the Sponsor will be immediately notified and the date and reasons for the withdrawal will be clearly stated in the volunteer's CRF.

Volunteers must be withdrawn under the following circumstances:

- if personal circumstances suggest that the visits required by the protocol cannot be guaranteed any longer,
- if adverse events (including intercurrent illnesses) develop, which rule out continuation of the study medication, or, due to impaired validity of the results, make it appear inadvisable to further participate in the study,
- **If Covid-19 PCR test result is positive, the volunteer(s) will be dropped out from study.**
- if subjects who have intaked or administrated of any prescribed systemic or topical medication (including OTC medication) within **2 weeks** of the start of the study (*except singles doses of analgesics which have no drug interaction with study products*) given in case of an adverse event (e.g. headache) during the study,
- if circumstances defined as exclusion criteria are registered,
- if administration of any drug is necessary, which is not permitted according to the exclusion criteria (see section 11.2), independently of its necessity due to the occurrence of adverse events (including intercurrent illnesses) or of its use due to other reasons,
- if vomiting occurs at or before 2 times median t_{max} .
- if diarrhea exists during screening and /or medication day.

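### The laboratory safety measure in section 19.1.4 counts out-of-range values without using the entry value, and the section names no safety set or denominator

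*Combined protocol and SAP*

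**What the plan says.** Adverse events and clinical and laboratory examinations are the safety endpoints (synopsis; section 13.8). How they are analysed is set out in section 19.1.4: "The assessment of safety will be based mainly on the frequency of AEs and on the number of laboratory values" outside pre-determined ranges, with other safety data considered as appropriate. No population, denominator, comparison with entry or allocation of events to Test or Reference is given.

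**Laboratory values.** Inclusion criterion 11 accepts "Laboratory results within normal range or clinically non-significant". Section 13.1 adds that a single out-of-range value is generally not a reason for exclusion if there are no symptoms, related values show no pathological process, and the investigator records it as clinically irrelevant. The flow chart (section 6) schedules clinical chemistry, haematology and urinalysis twice, at screening and at the final examination.

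**Populations.** Section 10 refers to 30 healthy "male subjects (intention to treat population) will receive one single oral dose" and then states: "Data of the subjects who have completed the study according to the Clinical Study Protocol will be used for analytical, pharmacokinetic and statistical evaluation". Section 19 opens with "The statistical analysis of the pharmacokinetic data described in this section corresponds with provisions" and continues: "Statistical analysis will be performed as a valid case analysis including all volunteers in which no major protocol deviations occurred", with the added condition that all primary target variables are available. Section 19.4 plans a descriptive analysis of the safety data in the case report forms, to be placed in the Clinical Raw Data.

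**Withdrawal.** Section 14.1 makes withdrawal mandatory "if vomiting occurs at or before 2 times median" tmax, "if diarrhea exists during screening and /or medication day", and for adverse events that rule out continuing the study medication. Drop-outs are not replaced (section 14.2).

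**The concern.** A count of out-of-range values at the end of a study answers a safety question only if values already out of range at the start are set aside. Here such volunteers are knowingly admitted, so the count mixes their existing deviations with anything that arises after dosing. The entry results that would separate the two are collected but have no role in the stated method.

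The second issue is who is counted. Section 19.1.4 sits inside a section whose one stated set is the valid cases, and the completer sentence in section 10 names statistical evaluation without limiting it to pharmacokinetics. Several mandatory withdrawal triggers are themselves tolerability outcomes. If someone applied the completer sentence to the adverse event tables, the volunteers with those events would drop out of the frequencies meant to describe them.

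**Working it through.** The plan states no figure on this point, so there is nothing to reproduce. The laboratory part is a scale calculation; the population part is a comparison of text followed by a conditional illustration.

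**1. Laboratory count**

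Inputs from the documents:
- Chemistry items in inclusion criterion 11: glucose, urea, uric acid, creatinine, eGFR, total bilirubin, sodium, potassium, calcium, chloride, AST, ALT, GGT, alkaline phosphatase, total protein = 15. CBC and urinalysis are left out because their components are not fully itemised there.
- Volunteers: 30.

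Assumptions, not in the documents: the pre-determined ranges are ordinary reference ranges, and a fraction q of values falls outside them with no drug effect.

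Expected flagged values at the final examination = 15 x 30 x q = 450q:
- q = 2%: 9
- q = 5%: 22.5
- q = 10%: 45

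Creatinine and eGFR are closely linked. Counting them as one item gives 14 x 30 x 5% = 21.

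This total does not say how many flags were already present at entry. At q = 5% the two extremes are:
- every out-of-range value persists from entry: 0 of 22.5 newly out of range;
- entry and final values are independent: 22.5 x 0.95 = 21.4 newly out of range.

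The old share therefore cannot be derived from the documents. An entry-to-final shift table would show it directly; the planned count cannot.

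**2. Allocation by product**

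Under TRTR/RTRT (sections 13.3 and 19.3) a completer's final sample follows two doses of Test and two of Reference, and no laboratory sample is scheduled between periods. A per-product laboratory comparison is therefore not possible.

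**3. Safety set: the sections side by side**

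| Section | Points towards completers | Points towards all dosed |
|---|---|---|
| 10 | Completers used for statistical evaluation, without limit | The 30 subjects carry an intention-to-treat label, with no analysis role |
| 13.1 | | The exclusion of withdrawn volunteers from statistics is worded for plasma samples |
| 19 | Valid-case rule heads the section that contains 19.1.4 | Opens on pharmacokinetic data; rule requires the primary pharmacokinetic variables |
| 19.4 | | Descriptive analysis of case report form safety data, no completer limit |
| 11.3, 15.3 | | Every adverse event goes on the case report form, including intercurrent illness with the drop-out sheet |

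No row fixes a denominator.

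**4. What the ambiguity could do (conditional)**

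Suppose 3 of the 30 volunteers are withdrawn for early vomiting or medication-day diarrhoea. The 3 is an assumption.
- All dosed: 3/30 = 10% (exact 95% CI 2.1% to 26.5%).
- Completers only: 0/27 = 0% (0% to 12.8%).

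Other counts over all 30 dosed: 1 gives 3.3%, 5 gives 16.7%.

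The chance that at least one volunteer is affected is 1 - (1 - p)^30, with p an assumed per-volunteer probability:
- p = 1%: 0.26
- p = 5%: 0.79
- p = 10%: 0.96
- p = 20%: above 0.99

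**The case against.** A reader might infer that completers are the only analysis set, that the safety evaluation leaves out volunteers withdrawn for adverse events, and that early vomiting and dosing-day diarrhoea must come out as zero. The documents do not support this. Section 10 also labels the 30 subjects an intention-to-treat population. Section 19 frames its rule for pharmacokinetic data. Section 19.4 describes the case report form safety data without a completer limit. Nor does the plan apply the section 10 sentence literally elsewhere: it would confine analytical evaluation to completers, yet sections 13.1 and 14.4 require drop-out samples to be analysed. All of this stands. What remains is that the denominator is unstated and the general sentence leaves room for a narrower reading.

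A reader might also infer that the laboratory count would be mostly pre-existing background. That is not shown: the 450q figure covers old and new chance values alike, and screening out clearly pathological values may lower q. A newly-out-of-range count would still contain new chance excursions. The investigator already judges out-of-range values in writing (section 13.1) and follows final abnormalities judged to be adverse events (section 13.3, final examination). These points limit the gain but do not justify leaving the entry value out of the summary.

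Finally, the adverse event illustration has no rate behind it. Section 7.6 lists diarrhoea as very common and vomiting as common, but its table includes entries such as immune reconstitution syndrome and does not describe single doses in healthy men. The objective is bioequivalence, no Test-versus-Reference safety comparison is planned, and serious adverse event reporting depends on no analysis set.

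**Conclusion.** The laboratory point holds on the text. The stated measure ignores an entry value that is collected, while volunteers with out-of-range entry values may be admitted, so existing and new abnormalities are counted together. Under the 5% assumption about 22 final chemistry values would be flagged with no drug effect; how these divide into old and new is unknown.

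The population point holds as an ambiguity only. Section 19.1.4 defines no safety set or denominator, and the completer sentence in section 10 could be read to drop volunteers withdrawn under section 14.1, although sections 19 and 19.4 point the other way. The contrast of 3/30 with 0/27 shows what the narrow reading would do at an assumed rate. It is not a property of the plan.

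Neither point touches the bioequivalence conclusion. Both are worth correcting because the data are already collected.

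**What to change.** - **Section 19.1.4, laboratory:** replace the plain count with entry-to-final shifts, reporting values newly outside range and showing separately those already outside range at entry. Present them overall and not per product. State which ranges apply.
- **Sections 10 and 19:** say that the completer and valid-case rules apply to the pharmacokinetic comparison only.
- **Section 19.1.4, adverse events:** define the safety set as every volunteer who took at least one dose, including those later withdrawn. Tabulate adverse events by last product taken, with the number of volunteers dosed with that product as denominator.

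No withdrawal rule, procedure or sample needs to change. The cost is protocol wording and one extra table layout. Reported adverse event frequencies may look slightly less favourable than under a completers-only reading.
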